#### 6.1.2 Health Outcomes Measures

Two questionnaires will be utilized in this extension study:

- Modified Treatment Benefit Scale (Modified TBS)
  - the proportions of patients whose condition is rated as either 'greatly improved' or 'improved' will be determined

Please refer to Attachment 12.4 for further details regarding these questionnaires.

## **6.1.4 Duration of Effect Measures**

The following 2 measures of duration of effect will be determined:

- time to patient request for retreatment
- time to patient qualification for retreatment

# **6.2** Safety Measures

- adverse events
- serious adverse events

[figure not shown]
## 6.3 Examination Procedures, Tests, Equipment, and Techniques

[figure not shown]
Once the parental/legal guardian consent, minor assent, and data authorization/protection forms have been obtained, and all the required inclusion and exclusion criteria at have been met, the patient will be considered enrolled in the study.

[figure not shown]
Evaluations should be performed by the same evaluator throughout the study whenever possible. If it is not possible to use the same evaluator to follow the patient, then it is preferable to have the evaluations overlap (examine the patient together and discuss findings) for at least one visit.

[figure not shown]
## 6.3.1 Latex Sensitivity or Allergy

Precautions for latex sensitivity or allergy will be taken in accordance with local site practice for any applicable procedures eg, urodynamics, blood sampling, as well as for the study treatment procedures.

[figure not shown]

### **6.3.12** Health Outcome Measures

The and the Modified TBS are both completed at weeks 6 and 12 after each treatment and at the qualification for retreatment visit (if the patient qualifies).

Questionnaires should be administered prior to the patient undergoing any procedure for any study visit and prior to study treatment and will be completed as described in Attachment 12.4. The same person(s) (patient or parent(s)/caregiver) should complete the questionnaires throughout the study where possible. For example, if the patient is able to complete the questionnaires themselves, they should complete all questionnaires themselves throughout the study. If a parent or caregiver will assist or complete on the patient's behalf, then this should be done throughout the study.

The versions of the questionnaires provided in the protocol (Attachment 12.4) are samples and will be replaced with the local language questionnaire for the country where the questionnaire will be administered.

# 6.4 Other Study Supplies

The following will be provided by Allergan:

- all supplies needed for urine pregnancy testing, blood and urine sampling (supplies for central laboratory urine analysis and urine culture and sensitivity)
- patient bladder diaries
- containers to measure volume of urine at first morning catheterization

The study sites will be responsible for providing the following supplies:

- prophylactic antibiotics required prior to study treatment
- sedatives and anesthesia for use during study treatment administration
- sterile saline (or other appropriate sterile fluid) for bladder visualization during cystoscopic procedures, and for reconstitution of study medication
- needles and syringes for reconstitution of study medication

- all necessary equipment to measure the required urodynamic parameters
- flexible or rigid cystoscope with injection port and needles for injection
- ultrasound for kidney and bladder assessment
- refrigerator to store dry/reconstituted study medication at a temperature of 2 to 8°C, monitored by a calibrated temperature recorder
- freezer (nonfrost free) to store immunogenicity serum samples at -20 ±5°C or below, monitored by a calibrated temperature recorder
- internet connection (high-speed connection) for eCRF completion

## 6.5 Summary of Methods of Data Collection

An IVRS/IWRS will be used to manage study medication inventory. Data will be collected using eCRFs via a validated electronic data capture system (EDC). Source documents will be used and stored at the sites, and may include a patient's medical records, hospital charts, clinical charts, patient chart, copy of the EDC file, as well as the results of diagnostic tests such as laboratory tests, ultrasounds, and urodynamics (if performed). A central laboratory will be used for the analysis of all blood and urine samples (only storage for immunogenicity samples). The data will be transferred via secure server to Allergan.

#### 7. Statistical Procedures

The final statistical analysis will be conducted when all patients have completed or exited the study. On completion and analysis of the preceding study (191622-120), an interim analysis of this study is planned; sites may be unblinded upon completion of the interim analysis. A detailed statistical analysis plan will be finalized prior to the first study database lock.

# 7.1 Analysis Populations

One analysis population will be used in the statistical analysis of this study: the BOTOX-treated population.

Data from the patients' participation in this extension study (191622-121) will be integrated with the corresponding patients' data from the preceding study (191622-120). Thus, the BOTOX-treated population will include all patients enrolled into the extension study who have received at least 1 BOTOX treatment over the course of the total evaluation period.

All efficacy and safety analyses will be based on the treatment actually received in each treatment cycle. Patients will be grouped to the nearest dose group (50, 100, or 200 U BOTOX) based on the dose actually received.

[figure not shown]
## 7.2 Collection and Derivation of Efficacy Assessments

The key efficacy measure is the number of daytime urinary incontinence episodes recorded in the bladder diary. The diary data will be collected by the patient/parent/caregiver over 2 consecutive days in the week prior to clinic visits.

In addition, the bladder diary will be used to record the urine volume at first morning catheterization and the occurrence of night time incontinence.

Two questionnaires will be utilized in this extension study:

- •
- Modified TBS

# 7.2.1 Efficacy Variables

The following efficacy variables are being assessed in this long-term extension study:

- change from baseline in daily average frequency of daytime urinary incontinence episodes
- change from baseline in average urine volume at first morning catheterization (mL)

- presence or absence of night time urinary incontinence
- •
- proportion of patients with a positive treatment response on the Modified TBS (ie, rating their condition "greatly improved")

The key efficacy variable is the change from baseline in daily average frequency of daytime urinary incontinence episodes (daytime is defined as the time between waking up to start the day and going to bed to sleep for the night). The daily average frequency of daytime urinary incontinence episodes is obtained using the total number of daytime urinary incontinence episodes recorded in a 2-day bladder diary divided by 2. Baseline is defined as the daily average frequency of episodes of daytime urinary incontinence prior to the initial study treatment in the preceding study, 191620-120. Each daytime period recorded in the bladder diary is normalized to represent a 12-hour period to account for differing durations of the daytime period. The daily average frequency of daytime urinary incontinence episodes will be adjusted by the normalized daytime period.

The timepoint of main interest is week 6 after each BOTOX treatment.

For the baseline and posttreatment data, a patient must have at least 1 day of diary data (defined as a day where there is 1 or more urinary episodes [eg, incontinence, catheterization, or voluntary void] during the daytime collection period [between waking to start the day and going to bed to sleep at night]). In the case of patients who partially complete their diary, providing that at least 1 valid diary day out of 2 is available, the 2-day frequency of daytime urinary incontinence will be prorated with the value from the valid diary day. If less than 1 diary day out of 2 has been completed, the frequency of daytime urinary incontinence will be considered as missing.

## 7.3 Hypothesis and Methods of Analysis

There will be no hypothesis testing in this long-term extension study. All data will be summarized with descriptive statistics and/or frequency tables.

### 7.3.1 Efficacy Analyses

The efficacy analysis will be based on the BOTOX-treated population. Week 6 after each treatment will be the timepoint of main interest and the efficacy variable of key focus is change from baseline in the daily average frequency of daytime urinary incontinence episodes. Data will be presented by BOTOX treatment cycle according to the dose received at that treatment cycle (grouped to the nearest dose group, ie, 50, 100 or 200 U BOTOX), as well as by an overall BOTOX group (ie, regardless of dose).

### 7.3.1.1 Efficacy Analyses for Daytime Urinary Incontinence Episodes

For each BOTOX treatment cycle, descriptive statistics will be provided for the daily average frequency of daytime urinary incontinence episodes at baseline and posttreatment visits. The change from baseline (arithmetic mean and least-squares [LS] mean) and the 95% confidence intervals (CI) of the arithmetic and LS mean change will be provided.

A responder analysis for daytime urinary incontinence will be performed using different thresholds of reduction from baseline. A patient will be considered a treatment responder if they have at least a 50% reduction from baseline in daytime urinary incontinence, however other thresholds will also be evaluated. The proportion of patients with  $\geq$  50%,  $\geq$  75%,  $\geq$  90%, and 100% reduction from baseline in daytime urinary incontinence will be presented by BOTOX treatment cycle for each posttreatment visit.

In addition the change from baseline and responder analyses will be performed using the normalized daily average frequency of daytime urinary incontinence episodes; these analyses will also be conducted without the normalization of the variable to a 12 hour daytime period.

# 7.3.1.2 Efficacy Analyses for the Average Urine Volume at First Morning Catheterization

For each BOTOX treatment cycle, descriptive statistics will be provided for the average urine volume at first morning catheterization at baseline and posttreatment visits as described in Section 7.3.1.1.

# 7.3.1.3 Efficacy Analyses for the Presence or Absence of Night Time Urinary Incontinence

[figure not shown]
For each BOTOX treatment cycle, the number and proportion of patients who experienced night time urinary incontinence on 0, 1, or 2 nights will be presented for baseline and posttreatment visits.

#### 7.3.1.4 Health Outcomes Parameters

Health outcomes questionnaires and measures will be analyzed according to scoring algorithms described in the detailed statistical analysis plan.

For the Modified TBS, the proportion of patients with a positive treatment response (defined as their condition being either "greatly improved" or "improved") will be presented and its 95% CI will be provided for each BOTOX treatment cycle at baseline and posttreatment visits.

### 7.3.1.6 Dose-response

Exploratory analysis may be performed to study dose-response based on the daily average frequency of daytime urinary incontinence episodes. Details for any dose-response analysis will be provided in the statistical analysis plan.

#### 7.3.1.7 **Duration of Effect**

Duration of treatment effect will be assessed as time from each study drug administration to request for retreatment. The time from the day of each BOTOX treatment to the request for the subsequent treatment will be estimated using the Kaplan-Meier survival method for each treatment group for each BOTOX treatment cycle. For those patients who did not request retreatment, their data will be censored using the date of their last study visit. The proportions of patients/parents/caregivers requesting retreatment in each BOTOX treatment cycle will also be presented.

In addition, time to qualification for retreatment will be presented and analyzed as described above for time to request for retreatment.

# 7.4 Safety Analyses

All safety analyses will be conducted on the BOTOX-treated population. Safety variables are adverse events, serious adverse events, physical examination, vital signs, laboratory tests (urinalysis, hematology and clinical chemistry), renal function, kidney and bladder ultrasound, concomitant medications, concurrent procedures, and pregnancy test for females who are postmenarche.

Medical Dictionary for Regulatory Activities (MedDRA) nomenclature will be used to code adverse events. For each adverse event reported, the number and percent of patients will be tabulated based on the preferred term. The tables will be generated by relationship to treatment as well as by primary system organ class and severity.

Data will be presented by BOTOX treatment cycle and grouped according to the actual dose received at that treatment cycle (grouped to the nearest dose group [50, 100, or 200 U BOTOX]), as well as by an overall BOTOX group (ie, regardless of dose).

## 7.5 Subgroup Analyses

For each BOTOX treatment cycle, descriptive statistics will be provided for the daily average frequency of daytime urinary incontinence episodes as described in Section 7.3.1.1 by investigator site, as well as by key demographic or baseline characteristics, including concurrent anticholinergic therapy (eg, use and nonuse), baseline daytime urinary incontinence episodes ( $\leq 6$  episodes or > 6 episodes over the 2-day diary collection period), age (< 12 years or  $\geq 12$  years), race, and sex.

## 7.6 Sample Size Calculation

The sample size calculation for this study is determined empirically. Approximately 100 patients are anticipated to roll over into this study, which is assuming approximately 76% of patients randomized into Study 191622-120 will be available and willing to participate in this study.

## 7.7 Interim Analyses

An interim analysis is planned to coincide with the completion and subsequent database lock of the main study, 191622-120. On completion of this interim analysis, the study will be unblinded to Allergan personnel. Study sites will be unblinded upon finalization of the interim clinical study report. Additional interim analyses may also be conducted. Further details of the interim analysis will be provided in the analysis plan.

# 8.1 Patient Entry Procedures

# 8.1.1 Overview of Entry Procedures

Prospective patients as defined by the criteria in Sections 4.3 and 4.4 (Inclusion/Exclusion Criteria) will be considered for entry into this study. Patients will roll over directly into this

study from the preceding study, 191622-120 (the exit visit of the preceding study will be the same as the entry visit for this extension study).

#### 8.1.2 Informed Consent and Patient Privacy

The study will be discussed with the patient/legally authorized representative and a patient wishing to participate or his/her legally authorized representative must give informed consent and, when applicable, minor assent prior to any study-related procedures or change in treatment. The patient/legally authorized representative must also give authorization (US only), data protection consent (Europe only), and other written documentation in accordance with the relevant country and local privacy requirements (where applicable) prior to any study-related activities or procedures.

As patients directly roll over from Study 191622-120 to this extension study, consent will have been obtained prior to the patient exiting the preceding study, 191622-120.

Further information is provided in Section 10.1.

[figure not shown]
Each patient who provides informed consent and/or assent will continue to use their IVRS/IWRS-assigned patient number from Study 191622-120 and this will be used on patient documentation throughout the study.

## 8.1.3 Procedures for Final Study Entry

Final study eligibility will be determined at the day 1 visit to confirm that the patient fulfills all the inclusion criteria without any exclusion criteria as specified in Sections 4.3 and 4.4 of the protocol.

Entry into this study is directly from the exit visit from the preceding study, 191622-120 (exit visit of Study 191622-120 equals day 1 for Study 191622-121), therefore procedures associated with the exit visit of the preceding study do not need to be repeated for entry into this study. Similarly, if a patient entered this extension study having qualified for retreatment in the preceding study, the qualification procedures do not need to be repeated in this study.

A patient is considered to have entered (ie, enrolled) into the study when they have met the study entry criteria.

#### 8.3 Instructions for the Patients

Patients/parents/caregivers will be instructed on the following:

- to strictly follow the study visit schedule and report any changes in condition to the investigative site
- to maintain the dose of any concurrent medication and anticholinergic medication during the study whenever possible (except anticholinergic medication which can be modified as described in Section 4.5.1)
- to remain on the same CIC regimen
- to change wet pads/diapers/underwear as soon as possible during diary collection periods in order to accurately capture episodes of incontinence
- to call the study site if they are experiencing any difficulties following study treatment administration or study procedures
- to contact the study site to report any hospitalizations
- to call the study site as soon as possible in order to reschedule, if the patient cannot make their next scheduled study visit
- diaries should be completed and brought to the study site at each scheduled clinic study visit

#### 8.4 Unscheduled Visits

Unscheduled visits can be performed if safety concerns arise and at the discretion of the investigator. Additional examinations may be performed as necessary to ensure the safety

and well being of patients during the study. eCRFs will be completed for each unscheduled visit.

### 8.5 Compliance with Protocol

Participating patients (or parents/caregivers) should be able to adhere to the diary completion and testing parameters as described in this protocol.

Data will be recorded on the appropriate eCRF supported by appropriate source documentation. At each visit, patients/parents/caregivers should be asked if any concomitant medications had been used, if they had undergone any concurrent procedures (non-study procedures), and their compliance with the protocol since the previous visit.

#### 8.6 Early Discontinuation of Patients

Patients may voluntarily withdraw from the study at any time. Patient discontinuation from the study and the reason for early discontinuation will be clearly documented on the appropriate eCRF. Patients who agree to follow-up will be followed for a minimum of 12 weeks after study treatment for safety as per the protocol. If a patient exits the study prior to study completion, all assessments for that visit should be performed in addition to any other exit visit assessments.

#### 8.7 Withdrawal Criteria

Patients have the right to withdraw from the study at any time and for any reason without prejudice to his or her future medical care by the physician or the institution. The investigator and Allergan also have the right to withdraw a patient from the study at any time for any reason.

Patients should be discontinued from the study if any of the following criteria are met. Where possible, the decision to withdraw a patient from study treatment or the study should be discussed with Allergan.

- patient develops (or has an exacerbation of) any medical condition that, in the opinion
  of the investigator, would put the patient at an unacceptable medical risk or
  compromises the patient's ability to participate in the study
- patient becomes pregnant (see Section 4.5.1.1 Definition of Females of Childbearing Potential and Acceptable Contraceptive Methods)

- patient/parent/caregiver is unwilling or unable to continue to comply with study procedures
- investigator requests a dose increase after the patient has received 2 treatments with 200 U BOTOX
- investigator assesses that the patient should not be retreated with the current dose, but that a dose reduction would be warranted

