#### Study Design

Structure: Multicenter, double-blind, long-term follow-up

*Duration*: Patients will participate in the study for at least 48 weeks following entry into the study and should have at least 12 weeks follow-up since the last treatment prior to exiting the study. The minimum duration is therefore 48 weeks, and the maximum duration is approximately 60 weeks (for patients who received their last treatment at week 48 with 12 weeks posttreatment follow-up).

Study Treatment Groups: There will be 3 dose options in this study: 50 U BOTOX (not to exceed 6 U/kg), 100 U BOTOX (not to exceed 6 U/kg), and 200 U BOTOX (not to exceed 6 U/kg). At each retreatment, the investigator can elect to keep the dose the same or increase the dose one level; if it is deemed that a dose reduction would be warranted then the patient should be exited from the study. (see Section 5.5 for further details). The dose decision will be based on the response to the previous treatment (for the first retreatment the reference treatment will be the initial treatment received in the preceding study). Both the preceding and subsequent dose will remain blinded until the interim analysis has been reported (see Section 7.7). The dosing options will depend on the investigator's decision as summarized below:

- Elect to keep the same dose as received at the previous treatment (dose not to exceed 6 U/kg)
- Elect to increase the dose compared to the previous treatment (dose not to exceed 6 U/kg):
  - o if the patient received 50 U at the previous treatment, they would receive 100 U
  - o if the patient received 100 U at the previous treatment, they would receive 200 U
  - o if the patient received 200 U at the previous treatment, they would remain at 200 U

However, if the investigator requests a repeat dose escalation despite the patient having received 2 doses of 200 U, the patient will be exited prior to receiving any further treatments and will be followed-up for a minimum of 12 weeks since their last treatment. In addition, if the investigator assesses that the patient should not be retreated with the current dose and that a dose reduction would be warranted, the patient should be exited from the study as a reduction of dose in this study is not an option. In such cases, the patient will be followed up for a minimum of 12 weeks since their last treatment.

Controls: None

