# 5.3 Methods for Blinding

Both patients and investigators will remain blinded to BOTOX dosage (unless the patient is requested to exit the study via the IVRS, as described at the end of Section 5.5, or until the interim analysis has been reported as described in Section 7.7).

The study medication will be packaged and labeled in identically appearing vials and reconstituted by an independent drug reconstitutor (IDR). The study medication will be identified as an investigational compound and the carton will also be labeled with the study number and kit number.

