# 5.5 Method for Assignment to Treatment Groups/Randomization

There will be no randomization in this long-term extension study.

All patients who receive treatment in this study will receive BOTOX. The blinded dose received (50, 100, or 200 U BOTOX, not exceeding 6 U/kg) will be dependent on the assessment of the clinical response (efficacy and safety) to the previous blinded study treatment (which will have been 50, 100, or 200 U BOTOX, not exceeding 6 U/kg). The patient/parent/caregiver will be questioned on their treatment response to establish if, in their opinion, the current treatment response is adequate or if there was little or no treatment benefit and whether they would be willing/want to have a higher dose. They will also be questioned on whether the patient is experiencing side effects. Using this information, the investigator will use his/her own clinical assessment of the patient and apply the following criteria for the retreatment dose request:

- if the benefit/risk balance is evaluated by the investigator to be appropriate at the current dose, then the same dose would be requested
- if the investigator assessed that, although the preceding dose was well tolerated, the
  response received was insufficient and warrants a higher dose, then a dose increase would
  be requested

• if the investigator assessed that there were side effects that would warrant a lower dose, the patient would be exited from the study

Compared to the previous treatment, the investigator therefore has the following options:

- elect to keep the same dose as received at the previous treatment (not to exceed 6 U/kg)
- elect to increase the dose compared to the previous treatment (not to exceed 6 U/kg):
- if the patient received 50 U BOTOX at the previous treatment, they would receive 100 U BOTOX
  - if the patient received 100 U BOTOX at the previous treatment, they would receive 200 U BOTOX
  - if the patient received 200 U BOTOX at the previous treatment, they would remain at 200 U BOTOX (after 2 requests to increase the dose from 200 U the patient will be exited; see below)

At the qualification for retreatment visit the investigator or designee will contact the IVRS/IWRS and indicate the treatment option for the patient. IVRS/IWRS options will be either to remain at the same dose or to increase the dose since patients will be exited from the study if the investigator assessed that a lower dose was warranted (see below).

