In the following 2 scenarios patients will be exited once a minimum of 12 weeks follow-up since their last treatment has occurred:

- if the investigator requests a dose increase on 2 occasions for a patient already receiving 200 U, the IVRS/IWRS will indicate upon the second request that the patient must be exited from the study and further retreatment will therefore not be received.
- if the investigator assesses that the patient should not be retreated with the current dose but that a dose reduction would be warranted, the patient should be exited from the study as a reduction of dose in this study is not an option.

Once all "day of treatment criteria" have been met at the day of treatment visit, the study medication will be allocated via IVRS/IWRS. Study medication will be labeled with medication kit numbers and the IVRS/IWRS will provide the IDR with a specific medication kit number and treatment group assignment for the patient.

The patient number used in Study 191622-121 will be the same as that allocated to the patient in the preceding study, 191622-120.

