## 5.10.1 Qualification for Retreatment Criteria

At each follow-up clinic visit and telephone contact from week 12 onward, the patient's treatment response will be discussed with the patient/parent/caregiver.

Patients/parents/caregivers can request retreatment at any scheduled clinic or telephone visit, or between scheduled visits. If a request is made at a scheduled clinic visit and all "qualification for retreatment criteria" are fulfilled, that clinic visit then becomes the qualification for retreatment visit and the additional procedures will be performed, otherwise a qualification for retreatment clinic visit should be conducted within approximately 1 to 2 weeks of the request for retreatment and the "qualification for retreatment criteria" should be assessed prior to performing any other procedures. The reason for the request will be collected. (Note that patients who qualified for retreatment in the preceding study, 191622-120, at which point they exited, do not need to be requalified to receive their first retreatment in this study).

In order to qualify for retreatment, the criteria listed below must be fulfilled:

- patient/parent/caregiver requests retreatment
- patient has a total of at least 2 daytime urinary incontinence episodes over the 2-day diary collection period
- at least 12 weeks has elapsed since previous study treatment
- patient has not experienced a serious treatment-related adverse event at any time

Once these criteria are fulfilled, the patient is considered qualified for retreatment; this does not need to be repeated (or any of the associated qualification for retreatment procedures) if the patient does not get treated at the subsequent treatment visit or the treatment visit is delayed.

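### Protocol Sections 8.7 and 5.5 give opposite instructions when a first increase request at 200 U follows a same-dose decision at 200 U

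*Protocol*

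**What the plan says.** Three places in the protocol state when a patient at the top dose level must leave.

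- **Section 8.7 (Withdrawal Criteria)** opens its list with "Patients should be discontinued from the study if any of the following criteria are met". One criterion is that the "investigator requests a dose increase after the patient has received 2 treatments with 200 U BOTOX". No earlier increase request is needed.
- **Section 5.5** lets the investigator choose the same dose or an increase at every retreatment. An increase request for a patient already at 200 U results in 200 U again, with the note that "after 2 requests to increase the dose from 200 U the patient will be exited". The closing part of the section adds that "the IVRS/IWRS will indicate upon the second request that the patient must be exited from the study".
- **The Protocol Summary** (Study Treatment Groups) exits the patient "if the investigator requests a repeat dose escalation despite the patient having received 2 doses of 200 U".

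Only Section 5.5 says what the IVRS/IWRS is to do; Section 8.7 does not mention the system. Section 5.3 states that "Both patients and investigators will remain blinded to BOTOX dosage", with exceptions for an IVRS-requested exit under Section 5.5 and for the period after the interim analysis is reported. Section 7.7 adds: "Study sites will be unblinded upon finalization of the interim clinical study report". The SAP (Section 1.1) refers to Section 5.5 when it describes blinding, but does not say which exit rule applies.

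**The concern.** One rule counts 200 U treatments received and the other counts increase requests made at 200 U. The two counts come apart as soon as a 200 U treatment follows a same-dose decision. A patient can then have had two 200 U treatments with no increase request made at that level. At the first such request Section 8.7 says withdraw, Section 5.5 says retreat, and both cannot be followed.

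What is at stake is whether a child has a further cystoscopic injection session or leaves the study. A blinded site cannot see the problem, because the Section 8.7 count depends on a dose the investigator does not know. Once sites are unblinded, an investigator could find that a withdrawal criterion has been met although Section 5.5 still allows retreatment. The rule also decides who appears as an exit, and who contributes another 200 U cycle, in the by-cycle disposition tables of SAP Section 3.2.

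**Working it through.** The plan has no figure to reproduce, so the check applies both rules to every possible sequence of decisions.

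**Inputs**
- Decisions at each retreatment: S (same dose) or I (increase), from Section 5.5.
- Dose steps: 50 to 100, 100 to 200, and 200 stays at 200 (Section 5.5).
- Reference dose for the first extension decision: the treatment given in the preceding study (Protocol Summary). A 200 U treatment there is counted as the first.
- Spacing: "at least 12 weeks has elapsed since previous study treatment" (Section 5.10.1).
- Last treatment: no later than week 48 after day 1 (Section 5.9.1).
- Assumption: the patient qualified in the preceding study, so the first decision falls on day 1, and later decisions come at the 12-week minimum. This gives weeks 0, 12, 24, 36 and 48, that is 48/12 + 1 = 5 decisions at most.

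**Rules as coded**
- Section 5.5: exit at the second I made while at 200 U.
- Section 8.7: exit at any I once at least two 200 U treatments have been received.
- Protocol Summary, read literally: exit when both conditions hold.

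**Earliest disagreement from each starting dose**

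| Preceding-study dose | Decisions | Week of the last decision | 200 U treatments received by then | Increase requests made at 200 U | Section 5.5 | Section 8.7 |
|---|---|---|---|---|---|---|
| 200 U | S, I | 12 | 2 (preceding study, week 0) | 1 | retreat | withdraw |
| 100 U | I, S, I | 24 | 2 (weeks 0, 12) | 1 | retreat | withdraw |
| 50 U | I, I, S, I | 36 | 2 (weeks 12, 24) | 1 | retreat | withdraw |

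These are the earliest possible weeks; treatment may follow qualification by up to 4 weeks, which moves them later.

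**Where the rules agree.** If the first decision at 200 U is I, the patient gets at least a second 200 U treatment before the next I. That next I is then both the second request and a request after two treatments, so both rules exit at the same point. If no increase is ever requested at 200 U, neither rule applies.

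**How many sequences conflict.** With m decisions left on reaching 200 U, a conflict needs S first and at least one I afterwards, which gives 2^(m−1) − 1 sequences. Over five decisions there are 2^5 = 32 sequences from each start:
- From 200 U (m = 5): 2^4 − 1 = 15 of 32.
- From 100 U (200 U reached at decision 1, 2 or 3, so m = 4, 3, 2): 7 + 3 + 1 = 11 of 32.
- From 50 U (second I at decision 2 in one way, or at decision 3 in two ways, so m = 3, 2): 1×3 + 2×1 = 5 of 32.

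Full enumeration gives the same counts. They count possible histories and are not probabilities. In no sequence did Section 5.5 exit a patient before Section 8.7, and Section 5.5 and the Protocol Summary never differed.

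**Sensitivity to the count.** If Section 8.7 counted extension treatments only, the conflict would not go away. From 200 U, S, S, I would still divide the rules (at week 24). The sequence I, I would also divide them, in the other direction: Section 5.5 exits at the second request, when only one extension treatment has been given.

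**The case against.** The best reply is that Section 8.7 is shorthand for Section 5.5, and that Section 5.5 is the working rule. Protocol Sections 3 and 5.3 and SAP Section 1.1 all point to Section 5.5 for the IVRS exit, and none points to Section 8.7. While the study is blinded, the site only enters same or increase and the system responds as Section 5.5 describes. In practice one answer results unless the system was specified from Section 8.7, which nothing in the documents suggests. The Protocol Summary gives the Section 5.5 result, so only one bullet differs. After unblinding, an investigator who knows the patient is at 200 U has little reason to request an increase that cannot be given, and Section 8.7 asks that withdrawals be discussed with the sponsor where possible.

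Much of this stands as a limit on the practical risk: divergent conduct during blinding is unlikely, and the post-unblinding route is the weaker one. It does not remove the conflict. The pointers to Section 5.5 concern blinding and set no precedence. Section 8.7 makes any single criterion sufficient and carries no reference to Section 5.5 on this item, although its pregnancy item does name its source section. If the system follows Section 5.5, a patient is retreated while a written withdrawal criterion is met. Discussion with the sponsor can settle a single case but does not supply a rule.

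**Conclusion.** The concern holds. Sections 8.7 and 5.5 contradict each other on one pattern: a same-dose decision at 200 U that comes before the first increase request at 200 U. The direction is always the same, with Section 5.5 allowing another 200 U treatment (other criteria being met) and Section 8.7 withdrawing the patient. The pattern can be reached from every starting dose within the 48-week window, at the earliest at week 12, 24 or 36.

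This rests on counting the preceding-study treatment towards the Section 8.7 total, which is the natural reading given the Protocol Summary, and on the shortest permitted schedule. The number of patients affected cannot be derived from the documents.

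The statistical effect is small. Protocol Section 7.3 plans no hypothesis testing. The paired comparison in SAP Section 5.2 covers only increases from 50 to 100 U or from 100 to 200 U. Summaries by dose received can be produced under either rule. The point should be fixed because it governs retreatment or exit of a child, not because an estimate is at risk.

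**What to change.** Reconcile Section 8.7, both statements in Section 5.5 and the Protocol Summary to one exit rule in identical words. The rule should say whether it counts requests, treatments or both, and whether a 200 U treatment in the preceding study counts. A cross-reference from Section 8.7 to Section 5.5 would keep them aligned. Then confirm that the IVRS/IWRS specification applies that rule. The choice of rule belongs to the sponsor's clinical team and is not proposed here.

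The cost is clarification wording in the protocol and one check of the system specification. No planned analysis needs to change.
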